12.4 Safety Endpoints

The following will be evaluated as safety endpoints: AEs, clinical parameters (HR, BP, vital signs), laboratory parameters (clinical chemistry and hematology) and survival.

12.5 Synopsis of Key Statistical Approaches

12.5.1 Primary Efficacy Comparison

The primary efficacy comparison involves testing the following one-sided superiority hypotheses: **H₀: $\pi_{0.50} - \pi_{\text{placebo}} \leq 0$ vs H_a: $\pi_{0.50} - \pi_{\text{placebo}} > 0$** ; where $\pi_{0.50}$ and π_{placebo} represent the true probability of freedom from durable loss of kidney function (alive, free of dialysis, and less than a 37% loss of eGFR (measured with the MDRD formula from the patient's reference eGFR)) at Day 28. Each probability represents the proportion of subjects on each arm expected to achieve freedom from durable loss of renal function. These

hypotheses will be tested using an unadjusted chi-square test at a one-sided type 1 error rate of $\alpha=0.025$. The null hypothesis will only be rejected if the proportion of responders is larger in the active drug group compared to placebo. It is a noteworthy advantage of the sample size re-estimation approach to be used (see details below) that the conventional test statistic may be used to test the primary hypothesis and there is no need to weight subjects randomized after the sample size re-estimation differently from those randomized before the sample size re-estimation.

12.5.2 Sample Size Justification

This trial will enroll 120 subjects who will be randomized in a ratio of 1:1 to either Reltecimod 0.50 mg/kg or placebo, each in addition to SoC. Sample size analysis was performed assuming that all patients will be evaluable for the primary endpoint using last observation carried forward (LOCF) for patients missing creatinine on Day 28. The primary efficacy hypothesis will be tested using an unadjusted χ^2 statistic with a one-sided $\alpha=0.025$ significance level. Rejection the null hypothesis will only occur if investigational drug superiority is demonstrated. Statistical power was computed for a range of expected treatment group differences supported by the results of preliminary studies. Table 6 summarizes the statistical power for a fixed sample design with a total sample size of $N=120$ (60 per group) for various assumptions regarding the success rate in the investigational arm and assuming a success probability of 0.50 among controls. This sample size results in 81.6% power if the true success rates are 75% and 50% for the investigational and placebo, respectively, a group difference of 25%.

12.5.3 Sample Size Re-Estimation

A “Promising Zone” sample size re-estimation (SSR) interim analysis (IA) is planned for when between 50% and 67% of the initial sample size is evaluable for the primary efficacy endpoint (Mehta and Pocock 2011)⁵³. The purpose of the SSR is to maintain (conditional) power when the treatment group difference is smaller than 0.25, but still clinically meaningful.

A pre-specified maximum sample size expansion will be specified prior to providing unblinded results to the iDMC but in no case will the sample size expansion exceed an additional 200 subjects. With this restriction, only clinically meaningful treatment effects are detectable with good statistical power at the maximum sample size. The specific rules for determining if sample size expansion is permissible and if so, by how much, will ensure control of type 1 error.

Specifically, the sample size will be increased up to the maximum to maintain conditional power to as close to 80% as possible, but only if conditional power at the interim analysis is above a pre-specified threshold that results in control of type 1 error to the desired nominal value. If conditional power falls within the Promising Zone, increasing the sample size up to the pre-specified maximum is at the discretion of the Sponsor.

The pre-specified conditional power threshold is the lower bound of the Promising Zone and its value may be obtained from Table 1 in Mehta and Pocock 2011. It depends on the ratio of the maximum sample size to the initial sample size (1.5, 2, 3, or infinite), the

fraction of the initially planned sample size included in the IA for SSR (0.25, 0.5, or 0.75), and the level of conditional power to be maintained (80% or 90%). Additional scenarios can be determined using linear interpolation. For 80% power, the lower bounds of the Promising Zone range from 0.30 to 0.42 depending on these three parameters. If conditional power falls within the Promising Zone, increasing the sample size up to the pre-specified maximum up to the discretion of the Sponsor.

Table 6 provides a simple evaluation of how the size of maximum sample expansion relates to statistical power for detecting various clinical effect sizes. Table 6 compares statistical power for fixed sample designs with total sample sizes of 120 (the initially planned sample size), 180 (allowing up to 60 more subjects), and 320 (allowing up to 200 more subjects). The selected maximum will be no larger than 200 additional subjects. As noted above, a fixed sample size design randomizing 120 subjects achieves 81.6% power if the treatment group difference is 25% (i.e., 75% versus 50%). Similarly, a fixed sample size design with 180 subjects achieves 82.7% power if the treatment group difference is 21% (i.e., 71% versus 50%). Finally, a fixed sample size design with 320 subjects achieves 82.9% power if the treatment group difference is 16% (i.e., 66% versus 50%). A 16% treatment group difference is still considered clinically meaningful. Therefore, even if a maximum increase of 200 is selected, the study will only have large statistical power to detect clinically meaningful treatment effects.

Additionally, the lower bounds of the Promising Zone when the IA for SSR is performed with 67% of the initially planned sample size is 0.39 when the maximum increase is 60 subjects; but is reduced to 0.31 when the maximum increase is set to 200. If the observed proportions of responders are 0.66 (0.65) and 0.50 for active and placebo subjects, respectively, conditional power will be 0.3905 (0.3148). Therefore, in any case, the observed treatment group differences will need to be larger than about 0.15 depending on the scenario, for any sample size expansion to be even allowed under the Promising Zone approach. This makes it unlikely that the treatment group difference will be found to be statistically significant unless the true treatment effect exceeds about 0.15.

Table 6: Examples of power for fixed sample design (1-sided $\alpha=0.025$)

Control	Reltecimod	Power (N=120)	Power (N=180)	Power (N=320)
0.5	0.60	0.194	0.269	0.435
0.5	0.61	0.226	0.316	0.508
0.5	0.62	0.261	0.367	0.581
0.5	0.63	0.299	0.420	0.651
0.5	0.64	0.339	0.475	0.717
0.5	0.65	0.382	0.530	0.777
0.5	0.66	0.426	0.586	0.829
0.5	0.67	0.472	0.641	0.874
0.5	0.68	0.518	0.693	0.909
0.5	0.69	0.565	0.742	0.937
0.5	0.70	0.611	0.787	0.958
0.5	0.71	0.656	0.827	0.973
0.5	0.72	0.700	0.863	0.983
0.5	0.73	0.741	0.894	0.990
0.5	0.74	0.780	0.919	0.994
0.5	0.75	0.816	0.940	0.997

12.5.4 Futility Analysis

In addition to sample size re-estimation, a non-binding futility analysis will be conducted at the time of the interim analysis. If conditional power is below a pre-specified futility threshold, enrollment may be immediately stopped at the discretion of the Sponsor. The pre-specified threshold will be determined prior to unblinding the data for the interim analysis.

12.5.5 Control of Blinding and iDMC

This study will remain blinded as to treatment allocation. The actual randomized treatment allocations will be kept by a contracted third-party responsible only for managing the randomization process. A variable indicating the blinded treatment allocations will not be part of the clinical study data to be managed by the data management contract research organization (CRO). Therefore, only blinded study data will be available to the primary study statistician and responsible primary programming staff.

An iDMC will be utilized in this study. A detailed iDMC charter will be provided to clarify all relevant issues relating to fire-walls to protect against potential operational biases. The charter will provide decision rules, composition of the iDMC members and their conflict of interest statements. A separate unblinded interim analysis statistician will work with the

iDMC to provide unblinded data as necessary for iDMC deliberations. The unblinded statistician will determine the interim analysis conditional power and summarize the implications to members of the iDMC. The iDMC will inform specifically designated individuals from the Sponsor whether conditional power is below the futility zone, above the futility zone but below the Promising Zone, within the Promising Zone, or above the Promising. If within the Promising Zone, the iDMC will be informed as to the increase in sample size required to maintain conditional power to at least 80%, or if this is not possible, that the maximum allowed increase in sample size may be enrolled. The iDMC will then inform specifically designated Sponsor representatives of their recommendations based on the *a priori* plan.

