7.2 Allocation of Treatment, Randomization and Study Drug Administration

The pharmacist (or unblinded study-nurse/physician if performing study drug preparation at individual institution) will get the treatment allocation via fax and email notification after randomization in the RAVE™ EDC by site personnel available only to the study pharmacist (or unblinded study-nurse/physician if performing study drug preparation at individual institution). All other study-related personnel, hospital care givers, the Sponsor and the patient will remain blinded.

Following allocation of treatment, the study pharmacist (or unblinded study-nurse/physician if performing study drug preparation at individual institution) will prepare the study drug.

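### Protocol 12.5.5 tells the sponsor which of two continue-to-120 zones the interim result fell in, which serves no decision and gives away a range for the interim difference

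*Protocol*

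**What the plan says.** Protocol 12.5.3 plans a Promising Zone re-estimation, "planned for when between 50% and 67% of the initial sample size is evaluable for the primary efficacy endpoint". If conditional power falls in the zone, raising N up to a pre-set maximum is left to the sponsor. Protocol 12.5.4 adds a non-binding futility rule: below a threshold to be fixed before the interim unblinding, the sponsor may stop enrolment. The protocol describes no early stop for efficacy and no other action.

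Protocol 12.5.5 then sets out what leaves the iDMC. It is to "inform specifically designated individuals from the Sponsor whether conditional power is below the futility zone, above the futility zone but below the Promising Zone". The two remaining messages are that conditional power lies inside that zone or exceeds it. The same paragraph has the iDMC pass its recommendations, under the pre-set plan, to designated sponsor representatives. It leaves fire-walls to a charter that is not among the documents.

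SAP section 1 says the SAP prevails where the two documents differ. The SAP mentions re-estimation only in passing, in section 2.4. It has no zones, no conditional-power rule and no disclosure rule, so it neither changes nor withdraws 12.5.5.

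**The concern.** Set the four messages against the actions they lead to:

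| Zone reported to the sponsor | Action in the protocol |
|---|---|
| Below futility | Sponsor may stop (12.5.4) |
| Above futility, below Promising | None stated: continue to 120 |
| Promising | Sponsor may increase N (12.5.3) |
| Above Promising | None stated: continue to 120 |

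The second and fourth rows lead to the same action but reflect opposite results. Telling them apart supports no pre-specified decision, and the action already travels in the separate recommendation.

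What is at stake is operational bias. Designated people at the sponsor would know during enrolment whether the drug looks weak or strong. Some choices could still be open then. The SAP need only be final before the treatment codes are unblinded (SAP 1). It leaves the use of the mITT set partly to judgement (SAP 2.3). Protocol 15.7.2 also lists evidence of lack of efficacy as a ground for termination, separate from the futility threshold.

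**Working it through.** **Inputs.**
- N = 120, 1:1, so 60 per arm (12.5.2: "This trial will enroll 120 subjects who will be randomized in a ratio of 1:1").
- One-sided alpha 0.025, unadjusted chi-square (12.5.1). The SAP uses one-sided 0.05 (SAP 2.1.1 and 5.2).
- A look at 67% is 80 patients, 40 per arm, so t = 40/60 = 2/3.
- Lower edge of the Promising Zone at that look: "0.39 when the maximum increase is 60 subjects; but is reduced to 0.31 when the maximum increase is set to 200" (12.5.3).
- Upper edge: conditional power (CP) 0.80, inferred from the 80% target in 12.5.3.
- Futility threshold: not stated. Assumed range CP 0.05 to 0.20.
- Placebo rate 0.50, as in the protocol's own example.

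**Formula.** For an observed difference d = pT - pC with n1 = 40 per arm:
- SE = sqrt{[pT(1-pT) + pC(1-pC)]/n1}, z1 = d/SE
- CP under the observed trend = Phi{[z1/sqrt(t) - z(1-alpha)]/sqrt(1-t)}

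**Reproducing the plan's figures.** Section 12.5.3 states: "If the observed proportions of responders are 0.66 (0.65) and 0.50 for active and placebo subjects, respectively, conditional power will be 0.3905 (0.3148").
- d = 0.16: SE = sqrt[(0.2244 + 0.25)/40] = 0.1089; z1 = 1.4692; CP = Phi[(1.7994 - 1.9600)/0.5774] = Phi(-0.278) = 0.3905.
- d = 0.15: SE = sqrt[(0.2275 + 0.25)/40] = 0.1093; z1 = 1.3729; CP = Phi[(1.6814 - 1.9600)/0.5774] = Phi(-0.482) = 0.3148.

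Both match. A pooled variance gives 0.3747 and 0.3029, so the protocol used the unpooled form.

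**Reading zones back as observed differences.** Solving the same formula for d at each edge, with 40 per arm and placebo at 50%:

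| Edge | CP | d, one-sided 0.025 | d, one-sided 0.05 |
|---|---|---|---|
| Futility (assumed) | 0.05 to 0.20 | 9.1 to 13.2 points | 6.3 to 10.5 points |
| Promising, lower (max +200) | 0.31 | 14.9 points | 12.2 points |
| Promising, lower (max +60) | 0.39 | 16.0 points | 13.3 points |
| Promising, upper | 0.80 | 21.3 points | 18.8 points |

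The last column keeps the protocol's CP bounds. The documents give none for 0.05.

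**Sensitivity at 0.025.**
- With placebo at 40% or 60%, the Promising edges move by less than 1.5 points.
- At a 50% look (30 per arm), using the protocol's overall range of 0.30 to 0.42 for the lower bound, the edges are 14.2 to 16.2 and 22.2 points.

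**Precision of what is disclosed.** The SE is about 0.11, so a 95% interval around the interim difference is about ±1.96 × 0.109 = ±21 points.

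**The case against.** Several points on the other side stand.

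- **Two of the four zones must be disclosed.** The sponsor decides on futility stopping and on expansion, so it has to learn that those zones apply. A reader might infer that all zone reporting is avoidable. The protocol's decision rules do not support that. In the Promising Zone the recommended N says more than the zone name: by the standard formula for restoring 80% CP (not given in the documents), with a maximum of 320, a total of about 253 implies a difference of about 16 points and about 182 implies about 18.
- **The disclosure is limited.** It is a range for a noisy interim estimate and goes only to designated individuals. A reader might infer that each middle message pins the effect to about 5 points. That width rests on an assumed futility bound for one zone (about 2 to 7 points over the range above) and, for the other, counts the Promising Zone, where disclosure is unavoidable. Neither locates the true effect.
- **No contradiction with the blinding text.** Protocol 7.2 says "All other study-related personnel, hospital care givers, the Sponsor and the patient will remain blinded". A reader might set that against 12.5.5, but 7.2 concerns individual allocations sent to the pharmacist, not aggregate interim results.
- **The route to bias is a risk, not shown.** Care staff, the primary statistician and the programmers are blinded. The endpoint is death, dialysis and creatinine-based eGFR, derived by algorithm in the SAP. Someone who knows a zone but no allocations cannot steer effort by arm.
- **The charter may narrow the recipients.** It could do so, but removing the disclosure would contradict the explicit wording of 12.5.5.

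None of this supplies a reason to tell the sponsor which of the two continue zones applies.

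**Conclusion.** The concern holds for one split only: below Promising (but above futility) versus above Promising. Both lead to 120. At a 67% look, one-sided 0.025 and placebo at 50%, separating them tells designated sponsor individuals whether the observed difference is under about 15-16 points (down to about 9-13 if the futility bound is CP 0.05 to 0.20) or at least about 21. At the SAP's 0.05 with the same CP bounds, the edges are about 12-13 and 19 points.

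This rests on CP under the observed trend, which reproduces the protocol's figures, on 0.80 as the upper edge, and on the assumed futility range. It is an avoidable operational-bias risk, cheap to remove. It is not an error in the test, and nothing in the documents shows that bias would follow.

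**What to change.** In protocol 12.5.5 and the iDMC charter, replace the two messages for the zones with no sponsor action by a single one: continue to the planned 120. Keep the other two as they are in substance: the futility threshold has been crossed (non-binding, sponsor's discretion), or the sample size may be increased to N. Do not reword the futility message as an iDMC recommendation to stop, since that would change who decides. State that the zone and the conditional power stay with the iDMC and its unblinded statistician until database lock.

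The cost is a wording change in two documents. N, alpha and power are unaffected. The designated sponsor individuals lose the knowledge of which continue zone applies, which no stated decision uses.

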12.6 Summary of Other Elements of Analysis Plan

12.6.1 Randomization

120 patients will be recruited into the study and randomized to either 0.50 mg/kg Reltecimod or placebo in a 1:1 ratio. Randomization will be performed within site and according to two stratification variables:

- **Acuity of AKI:** whether or not AKI is diagnosed at time of presentation of abdominal infection or surgically confirmed NSTI; or during the 48 hours the suspected diagnosis of abdominal infection or surgical confirmation of NSTI.
- **Subject Age:** ≥ 18 to ≤ 75 or > 75 to ≤ 85 years old.

Four computer generated, blocked randomization lists will be provided for each site, one for each of four strata defined on the basis of the 2 by 2 cross-tabulation of the two stratification variables. Within each block, half of the assignments will be to active drug and half to placebo, in random order. Block sizes will be varied.

12.6.2 Patient Populations

The following analysis sets are defined:

- **Intent-to-treat (ITT):** The ITT analysis set will include all randomized patients.
- **As-Treated (AT):** The AT analysis set will include all randomized patients who were exposed to study medication (active or placebo). The AT analysis set will be used in primary safety analyses with patients assigned to actual treatment received.
- **Modified Intent-to-treat (mITT):** The mITT analysis set will include patients who were exposed to study medication and who had a definitive diagnosis of abdominal sepsis or NSTI with patients assigned to their intended randomized assignment. The mITT analysis set will be used in primary effectiveness comparisons.
- **Per Protocol (PP):** Optionally, a PP analysis set may be used in secondary effectiveness analyses. The PP analysis would include patients in the mITT analysis set assigned according to actual treatment received and excluding patients with either 1) significant violations of inclusion or exclusion criteria

with potential to confound estimates of drug effects or 2) post randomization protocol violations or intercurrent events with potential to confound estimates of treatment effects. Exclusions from the PP analysis set will be determined based on blinded clinical data. The PP analysis may be further restricted to include patients that survive at 3 least days when evaluating critical care variables.

12.6.3 Preliminary and Descriptive Analyses

Before proceeding with between-group comparisons of primary and secondary clinical endpoints, data quality will be assessed by descriptive summaries and graphical methods (e.g., histograms and scatterplots) in order to examine assumptions such as normality that underlie statistical models. Transformations will be used, if needed, to produce variables that conform to the distributional assumptions underlying the analytic techniques employed. Descriptive analyses will be performed in order to characterize the treatment groups and to confirm that the randomization resulted in no clinically significant group differences at baseline. Although emphasis will be on clinical significance, baseline comparisons will include t-tests or Wilcoxon rank sum tests as appropriate for interval variables and chi-square or Fisher's exact tests as appropriate for nominal variables to aid in the screening for baseline differences. Similarly, changes in clinical endpoints over time will be summarized within each treatment group using summary statistics including mean and median change scores, standard deviations and ranges. Pearson or Spearman rank correlation coefficients will be used to characterize associations among variables within treatment group. When summarizing across groups, partial correlations may be computed controlling for treatment group. For time-to-event outcomes (i.e., event-free survival), descriptive analyses will include construction of group specific Kaplan-Meier survival curves as appropriate

12.6.4 Secondary Endpoints

Secondary endpoints have been specified from several domains. Additional secondary endpoints include SOFA over time, time to the primary endpoint, critical care and hospital stay parameters (hospital length of stay (LOS), ICU and ICU-free days, ventilator days and –free days, vasopressor days and –free days). Analyses for these endpoints will generally be descriptive, with emphasis on characterizing clinical effect sizes. Nominal p-values will be presented. Categorical outcomes will be described using counts and percentages with nominal p-values determined through chi-square or exact methods. Critical care and hospital stay endpoints will be described using non-parametric approaches including using concordance statistics to characterize clinical effect sizes and Wilcoxon rank sum tests to determine nominal statistical significance. Methods appropriate for time-to-event endpoints including survival and life-table methods will be used for time-to-recovery endpoints.

12.7 Sub-group Analysis

Subgroup analysis will be performed. The primary subgroup analyses to be performed include:

Patients presenting with either Stage 2 or Stage 3 AKI.

By acuity of AKI (i.e., whether or not AKI is diagnosed at time of presentation of abdominal infection or surgically confirmed NSTI, or during the 48 hours from the suspected diagnosis of abdominal infection or surgical confirmation of NSTI).

By subject age ≥ 18 to ≤ 75 or >75 to ≤ 85 years old.

For these sub-group analyses, active dose versus placebo differences in likelihood of freedom from durable loss of renal function will be evaluated as well other selected secondary endpoints.

Other sub-groups to be evaluated will include patients who developed AKI up to ≤ 24 hours or 25-48 hours after the suspected diagnosis of abdominal infection or surgical confirmation of NSTI or if AKI diagnosed via creatinine criteria vs urine output criteria.

